8.12 Biomarkers

Biomarkers are not evaluated in this study.

9. Statistical Considerations

9.1 Statistical Hypotheses

9.1.1 Lead-in Phase

Descriptive analyses will be provided for the lead-in phase without formal hypothesis testing.

Page: 58 of 86

The findings from the lead-in phase of the study will be reviewed by the Sponsor to interpret the results from the lead-in phase and guide a decision on the conduct or not of the randomized phase as well as potential changes in the study design. The conduct of the randomized phase is contingent on conditions described in Section 4.1.

9.1.2 Randomized Phase

The randomized phase will test the Null Hypothesis of no difference between the darolutamide arm and the enzalutamide arm on the primary endpoint of mean percent change in Testosterone from baseline to week 12, against the alternative hypothesis of a difference between arms at a two-sided 0.05 level. For mean percent changes of Δ_D and Δ_E in the darolutamide and enzalutamide arms these hypotheses can be expressed as

$$H_0$$
: $\Delta_D = \Delta_E vs. H_1$: $\Delta_D \neq \Delta_E$

9.2 Sample Size Determination

9.2.1 Lead-in Phase

Approximately 25 participants will be assigned to darolutamide to achieve at least 20 evaluable participants. This sample size will help estimate the mean percent change in serum testosterone level at 12 weeks with a 95% confidence interval having a half-width of no more than 25%, assuming a true mean percent increase of less than 45% and a standard deviation of 65%. This assessment uses a log normal distribution for percent change.

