The conduct of the randomized phase is contingent on the results of the lead-in phase unless data from other ongoing studies could provide similar evidence. Participants will receive darolutamide 600 mg bid or enzalutamide 160 mg once daily for a total duration of 52 weeks until unacceptable toxicity, PSA progression, withdrawal of consent, investigator's or patient's decision to stop therapy, Sponsor's decision to terminate the study, or death. Following the 52-week intervention, all participants will be offered to continue the treatment with darolutamide as per investigator decision, including patients randomized to enzalutamide who would switch to treatment with darolutamide.

Page: 19 of 86

Study Intervention Lead-in phase

Study Intervention	Darolutamide
Dosage Level(s)	Darolutamide 600 mg (2 tablets of 300 mg) will be administered twice daily with food, equivalent to a total daily dose of 1200 mg
Route of Administration	Oral (p.o.)
Use	Experimental

Study Interventions Randomized phase

Study Intervention	Darolutamide
Dosage Level(s)	Darolutamide 600 mg (2 tablets of 300 mg) will be administered twice daily with food, equivalent to a total daily dose of 1200 mg
Route of Administration	Oral (p.o.)
Use	Experimental

Study Intervention	Enzalutamide
Dosage Level(s)	Enzalutamide 160 mg will be administered once daily with or without food
Route of Administration	Oral (p.o.)
Use	Experimental

The expected study duration for the lead-in phase is 18 months assuming 20 evaluable participants are enrolled within an enrollment period of 6 months and treated for 12 months (52 weeks). The expected study duration for the randomized phase is 25 months assuming 40 participants are enrolled within an enrollment period of 12 months. For each phase the primary analysis will be at 12 weeks. The final analysis for both phases will be conducted after all subjects have completed the 52 weeks of treatment and will analyze the long-term results of the secondary endpoints.

1.4.1.1 Lead-in phase:

).

During the lead-in phase 25 participants will be assigned in a single cohort to darolutamide to ensure that 20 participants treated with darolutamide for 12 weeks are evaluable for serum testosterone level at week 12. This sample size will help estimate the mean percent change in serum testosterone level from baseline at 12 weeks within at most +/- 25%, assuming a true mean percent increase of less than 45%. This assessment uses a log normal distribution for percent change.

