9.2.2 Randomized Phase

Contingent on the results of the evaluation in Section 9.1, the randomized phase statistical assumptions may be revised, or the study could be terminated after lead-in.

Should the study continue to the randomized phase unmodified, a maximum of 40 participants (20 per arm) will be randomly assigned to study treatment (darolutamide or enzalutamide) such that approximately 34 evaluable participants complete the study. The randomized stage will require a sample size of 20 per group to provide 85% power to test the null hypothesis of nodifference between groups on mean percent change at two-sided 0.05 level. This assessment is based on a mean percent change in testosterone from baseline and standard deviation for the darolutamide arm of 45% and 65% versus 110% and 75% respectively for enzalutamide and assumes a log normal distribution for percent change.

Page: 59 of 86

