4.8. Changes to Protocol-planned Analyses

There are no changes to the analyses described in the protocol.

ARAMON V3.0 Page: 20 of 31

5. Sample Size Determination

The sample sizes corresponding to the planned analysis methodology are provided below.

Lead-in Phase

Approximately 25 participants will be assigned to darolutamide to achieve at least 20 evaluable participants. This sample size will help estimate the mean percent change in serum testosterone level at 12 weeks with a 95% confidence interval having a half-width of no more than 25%, assuming a true mean percent increase of less than 45% and a standard deviation of 65%. This assessment uses a log normal distribution for percent change.

Randomized Phase

Contingent on the results of the evaluation in Section 1.2.1, the randomized phase statistical assumptions may be revised, or the study could be terminated after lead-in.

Should the study continue to the Randomized phase unmodified, a maximum of 40 participants (20 per arm) will be randomly assigned to study treatment (darolutamide or enzalutamide) such that approximately 34 evaluable participants complete the study. The randomized stage will require a sample size of 20 per group to provide 85% power to test the null hypothesis of no difference between groups on mean percent change at the two-sided 0.05 level. This assessment is based on a mean percent change in Testosterone from baseline and Standard Deviation for the Darolutamide arm of 45% and 65% versus 110% and 75% respectively for Enzalutamide and assumes a log normal distribution for percent change.

ARAMON V3.0 Page: 21 of 31

6. Supporting Documentation

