| 16 | 35.9 | 1.9 | | | |
| 17 | 36.8 | 1.9 | | | |
| 18 | 37.6 | 1.9 | | | |
| 19 | 38.5 | 1.9 | | | |
| 20 | 39.3 | 1.9 | | | |
| 21 | 40.2 | 1.9 | | | |
| 22 | 41.2 | 1.9 | | | |
| 23 | 42.1 | 1.9 | | | |
| 24 | 43.2 | 2.0 | | | |
| 25 | 44.3 | 2.0 | | | |
| 26 | 45.6 | 2.2 | | | |
| 27 | 47.1 | 2.3 | | | |
| 28 | 48.9 | 2.7 | | | |
| 29 | 51.3 | 3.0 | | | |
| 30 | 59.0 | 6.2 | | | |
| *SE = Standar | d Error on T-sco | re metric | | | |

PROMIS Physical Function 6b form

PROMIS Fatigue 8a form

ARAMON V3.0 Page: 27 of 31

Appendix 4: Randomized phase primary endpoint analysis for natural logarithm transformed Testosterone

Following data structure will be obtained for the Input dataset LN_DATA. LN_Change will be the difference between the LN(Testosterone) values at Visit 12 from the LN value at baseline.

```
Subjid trt LN_Change
Daro 0.5
Daro 0.9
ENZA 0.5
ENZA 0.8
```

The following SAS code will be used for the two-sample t-test.

```
PROC TTEST DATA=LN_DATA SIDES=2 ALPHA=0.05 H0=0;
CLASS TRT;
VAR LN_CHANGE;
RUN:
```

Appendix 5: Lead-in phase analysis for natural logarithm transformed Testosterone and other endpoints using the log transformation

For the primary end point analysis, PROC TTEST procedure similar to Appendix 4: Randomized phase primary endpoint analysis for natural logarithm transformed Testosterone will be used without the CLASS statement.

For the lead-in phase, the following data structure will be obtained for the input dataset LN_DATA to Proc Mixed. LN_Change will be the difference between the LN(Testosterone) values at Visit from the LN value at baseline. During the lead-in phase there will be no enzalutamide data.

```
Subjid trt
           visit LN Change
          WK2 0.5
     Daro
     Daro WK4 0.9
     Daro
          WK8 1.3
     Daro
          WK16 1.6
          WK24 1.7
     Daro
     Daro WK36 1.7
     Daro
          Wk52 1.6
     Daro
          WK2 0.4
     Daro WK4 1.3
```

Following PROC Mixed code will be used.

```
PROC MIXED DATA = LN_DATA;
CLASS VISIT SUBJID;
```

ARAMON V3.0 Page: 28 of 31

```
MODEL LN_CHANGE = VISIT /DDFM = KR;
RANDOM SUBJID;
REPEATED / TYPE = TOEP SUBJECT=SUBJID;
LSMEANS VISIT/ CL;
RUN;
```

Then the estimate for VISITS WK24 and WK52 will be retained. The dataset will have 2 lines. The fold change pair for each fold change (FC) can be computed as:

```
FC = EXP(Estimate);

LCL_FC = EXP(Estimate - StdErr*quantile('T', .975, DF));

UCL_FC = EXP(Estimate + StdErr*quantile('T', .975, DF));
```

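### The lead-in precision of 25% at 20 evaluable holds for a normal-quantile interval, not the planned t interval (about 27 points), and the 85% power at 20 per group is not restated for the 34 evaluable

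*Protocol*

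**What the plan says.** Protocol 9.2.1 plans about 25 lead-in participants "to achieve at least 20 evaluable participants" and says this size estimates the week-12 mean percent change "with a 95% confidence interval having a half-width of no more than 25%, assuming a true mean percent increase of less than 45" per cent, with an SD of 65% and a log-normal distribution. SAP section 5 repeats the claim: "95% confidence interval having a half-width of no more than 25" per cent. The synopsis (Protocol 1.4.1.1) words it as estimation "within at most +/- 25%, assuming a true mean percent increase of less than 45" per cent.

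The analysis is the back-transformed 95% interval of the mean log difference (Protocol 9.4.1.1, SAP 4.2.1.1). The protocol does not name the quantile. SAP Appendix 5 names the procedure: "For the primary end point analysis, PROC TTEST procedure similar to Appendix 4", without the CLASS statement, which gives a one-sample t interval.

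For the randomized phase, Protocol 9.2.2 says: "The randomized stage will require a sample size of 20 per group to provide 85% power". The inputs are 45% (SD 65%) for darolutamide and 110% (SD 75%) for enzalutamide, log normal, two-sided 0.05. The same paragraph caps randomization at 40, "such that approximately 34 evaluable participants complete the study". The primary test is a two-sample t-test on log differences in the evaluable population (Protocol 9.4.1.2, SAP 4.2). Protocol 9.4.1 describes the estimates as geometric means. Neither document says whether the planning means are arithmetic or geometric, and neither gives a log-scale SD.

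**The concern.** Precision is the only justification given for the size of the lead-in, and the interval that will be reported is wider than the one described. The lead-in is descriptive ("Descriptive analyses will be provided for the lead-in phase without formal hypothesis testing"), but its week-12 estimate decides whether the randomized phase is run, so readers will look at how precise that estimate is.

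The second part concerns the randomized phase. Its size and assumptions may be revised after the lead-in, which means comparing the observed log-scale SD with the planned one. That comparison needs the planning value and its scale in writing, and needs to be clear how the 85% relates to the number actually analysed. The two sample-size statements also use the same darolutamide inputs, so one reading ought to reproduce both.

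**Working it through.** **Inputs.** Darolutamide fold change 1.45, SD 0.65; enzalutamide fold change 2.10, SD 0.75; lead-in n = 20; randomized 20 per arm, or 34/2 = 17 per arm evaluable; two-sided 0.05 (Protocol 9.1.2, 9.2.1, 9.2.2). Equal division of the 34 is my assumption. The scale of the inputs is not given, so three readings are shown:

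- *Arithmetic:* log-SD s = √ln(1 + (SD/mean)²), giving √ln(1 + (0.65/1.45)²) = 0.428 and √ln(1 + (0.75/2.10)²) = 0.346. Geometric means (GM) = mean/exp(s²/2) = 1.323 and 1.978.
- *Geometric, ordinary SD:* GM 1.45 and 2.10, with s solved from GM²·exp(s²)·(exp(s²) − 1) = SD², giving 0.398 and 0.329.
- *Geometric, SD/mean taken as the coefficient of variation (CV):* GM 1.45 and 2.10, s = 0.428 and 0.346.

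**Lead-in half-width.** The interval is GM·exp(± q·s/√n). It is asymmetric, so half-width here means half the total width: 100·GM·sinh(q·s/√n).

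The plan's figure first, with arithmetic inputs and q = 1.960: 132.31 × sinh(1.960 × 0.4279/√20) = 24.96 points. The stated 25 is reproduced.

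The planned interval, with q = t(19 df) = 2.093: q·s/√n = 2.093 × 0.4279/4.472 = 0.2003. Lower arm 132.31 × (1 − 0.8185) = 24.0; upper arm 132.31 × (1.2217 − 1) = 29.3; half-width 26.7.

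| Reading (45%, n = 20) | Normal quantile | Planned t |
|---|---|---|
| Arithmetic | 24.96 | 26.7 |
| Geometric, ordinary SD | 25.4 | 27.2 |
| Geometric, CV | 27.4 | 29.2 |

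The condition that the true increase is below 45% helps only in part. On the arithmetic reading the t half-width at n = 20 is 25.9 at a true increase of 30%, 25.3 at 20% and 24.5 at 10%; it crosses 25 at about 16%. At a 45% increase it is 25.25 with 22 evaluable, 24.6 with 23 and 23.5 with 25. The synopsis wording of plus or minus 25 is not met even with the normal quantile, because the upper arm is then 27.3.

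**Randomized power.** Let D be the difference in mean log fold change, with pooled log-SD √((s₁² + s₂²)/2). Arithmetic: D = ln(1.978/1.323) = 0.402, pooled SD 0.389, D/SD = 1.032. Geometric: D = ln(2.10/1.45) = 0.370, pooled SD 0.365 (ordinary SD) or 0.389 (CV), D/SD = 1.014 or 0.951. The t column is the noncentral t with 2n − 2 df.

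| Reading | 17 per arm: normal / t | 20 per arm: normal / t |
|---|---|---|
| Arithmetic | 85.3% / 83.1% | 90.4% / 88.9% |
| Geometric, ordinary SD | 84.1% / 81.8% | 89.4% / 87.8% |
| Geometric, CV | 79.2% / 76.7% | 85.3% / 83.4% |

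The reading that gives 25 points (arithmetic, normal) gives 85% at 17 per arm, not at 20. The reading that gives 85% at 20 per arm (geometric CV, normal) gives 27.4 points in the lead-in.

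**The case against.** **The 25 is a legitimate planning approximation.** This stands. The figure reproduces with log-normal moments and a normal quantile, so a reader who infers a calculation error would be wrong. The fault is that the planned analysis uses a different quantile, which only SAP Appendix 5 makes explicit.

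**The 25% could be relative.** Neither document writes percentage points. As a relative margin on the fold change, the t interval at n = 20 is −18.1%/+22.2% (arithmetic and CV readings) or −17.0%/+20.5% (geometric, ordinary SD), which meets 25%. I think points is the natural reading, because the quantity is a mean percent change with its SD in the same units, but the text does not exclude the other.

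**The shortfall sits at a corner.** Also true. It is 1.7 points on the arithmetic reading, at the limiting increase and the minimum evaluable count. It is gone with 23 or more evaluable of the 25 planned on that reading, and with 24 on the geometric reading with an ordinary SD. On the CV reading, 27 would be needed.

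**The sample size behind the 85% is given.** A reader might infer that it is missing. It is not: both documents say 20 per group, and at that size t-test power is 83.4% to 88.9% across the three readings. What is missing is the link to the 34 evaluable.

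**A near-match exists.** Arithmetic means with the larger log-SD (0.428) in both arms give 24.96 points and 84.4% at 20 per arm by normal quantile. That is close, but it sets aside the stated enzalutamide SD, falls just short of 85%, and gives 82.5% by t-test.

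**Conclusion.** The point holds as a minor mismatch between the sample-size text and the planned analysis. Read in percentage points, the stated precision is not delivered by the planned t interval at 20 evaluable and a 45% increase: 26.7 points on the reading most favourable to the plan, up to 29.2 otherwise. On the arithmetic reading it is met only with a true increase of about 16% or lower, or with at least 23 evaluable. Power at the 34 evaluable is 83.1% by t-test on the arithmetic reading and 77% to 82% on the geometric ones, against the 85% stated for 20 per group.

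This rests on the 25% meaning points, on the three conversions to the log scale, on 17 evaluable per arm, and on the 34 being those with week-12 data. If more than 34 have week-12 testosterone, power lies between the two columns.

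A reader might go further and conclude that the lead-in is too small or the decision to proceed unsound. The documents do not support that. The decision uses the estimated mean percent change against 45%, not the width of the interval, and the interval reported will be valid whatever the planning text says.

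**What to change.** In Protocol 1.4.1.1, 1.4.1.2 and 9.2 and SAP section 5:

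1. Restate the lead-in precision for the t interval at 20 evaluable. If the inputs are arithmetic, this is about 27 points, roughly 24 below and 29 above the estimate at a 45% increase. Replace the symmetric plus-or-minus wording in the synopsis, and say that the figure is in percentage points if that is meant.
2. Give t-test power at 34 evaluable beside the value at 20 per group: about 83% and 89% if the inputs are arithmetic.
3. Say whether the planning means are arithmetic or geometric and give the log-scale SDs used (0.428 and 0.346 if arithmetic).

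The cost is a few sentences in each document and a stated lead-in precision about 2 points less favourable. Enrolment, the analysis and the 45% condition do not change.

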9.2.2 Randomized Phase

Contingent on the results of the evaluation in Section 9.1, the randomized phase statistical assumptions may be revised, or the study could be terminated after lead-in.

Should the study continue to the randomized phase unmodified, a maximum of 40 participants (20 per arm) will be randomly assigned to study treatment (darolutamide or enzalutamide) such that approximately 34 evaluable participants complete the study. The randomized stage will require a sample size of 20 per group to provide 85% power to test the null hypothesis of nodifference between groups on mean percent change at two-sided 0.05 level. This assessment is based on a mean percent change in testosterone from baseline and standard deviation for the darolutamide arm of 45% and 65% versus 110% and 75% respectively for enzalutamide and assumes a log normal distribution for percent change.

Page: 59 of 86

9.3 Populations for Analyses

For purposes of analysis, the following populations are defined:

Table 9-1: Populations for Analyses: Lead-in phase

Population	Description	
Screened	All participants who sign the informed consent form	
Evaluable	All enrolled subjects having testosterone data at baseline and week 12. Enrolled subjects include those who signed informed consent and met all inclusion and none of the exclusion criteria.	
Safety	All enrolled participants who received any darolutamide post-enrollment regardless of their eligibility for the study.	

Table 9-2: Populations for Analyses: Randomized Phase

Population	Description	
Screened	All participants who sign the informed consent form	
Evaluable	All randomized subjects having testosterone data at baseline and Week 12 who signed informed consent and met all inclusion and none of the exclusion criteria.	
Safety	All randomized participants who received any quantity of study intervention, regardless of their eligibility for the study. The safety evaluation will be performed based on the intervention actually received	

9.4 Statistical Analyses

This section is a summary of the planned statistical analyses of the primary and secondary endpoints. Additional exploratory analyses of the data will be conducted as deemed appropriate.

All baseline variables will be reported using the appropriate statistics: categorical variables by frequency tables (frequencies and percentages) and continuous variables by sample statistics (i.e., mean, standard deviation, minimum, median, quartiles, and maximum). The number of patients screened will be summarized for both the lead-in and randomized cohorts.

The primary analysis for the lead-in phase of the study will occur when the last participant has been on the treatment for at least 12 weeks, unless the participant discontinued due to lost to follow-up, withdrawal, or death. The primary analysis for the randomized phase will occur when all the patients in the randomized phase have been on the treatment for at least 12 weeks. Final analysis for both phases of the study will occur when the last participant on randomized phase has been on the treatment for at least 52 weeks after the start of study intervention, unless the participant discontinued due to lost to follow-up, withdrawal, or death. Separate analyses will be performed for the lead-in phase and the randomized phase of the study.

The statistical analysis plan (SAP) will be developed and finalized before database lock and will describe the participant populations to be included in the analyses and procedures for accounting for missing, unused, and spurious data.

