4.1 Overall Design

This is a two-stage open label phase 2 study with a lead-in single-arm phase and the randomized phase, to assess the impact of ARI darolutamide or enzalutamide as a monotherapy treatment on serum testosterone levels in men with hormone-naïve prostate cancer experiencing biochemical recurrence (BCR) after failure of treatment with curative intent for localized prostate cancer. Secondary endpoints to be evaluated include the impact of ARI monotherapy on energy metabolism and the metabolism of sex hormones as well as PSA response and safety. Exploratory endpoints will evaluate changes in bone metabolism, physical function, and quality of life profiles. The study design is shown in the Figure 4-1.

In the lead-in phase, approximately 25 participants will be treated with darolutamide for 52 weeks. The primary endpoint analysis of the lead-in phase will occur when all participants in the lead-in phase have been on treatment for 12 weeks, unless the participant discontinued due to lost to follow-up, withdrawal, or death. The secondary endpoint analysis of lead-in phase (see Table 3-1) will occur after patients have been treated for 52 weeks.

[figure not shown]
The study team will review the findings form the lead-in phase of the study, to provide input on interpretation of the results from the lead-in phase which will help guide a decision on the conduct or not of the randomized phase as well as potential changes in the study design for the randomized phase by the Sponsor. In any case, the conduct of the randomized phase is conditional on obtaining a mean percent change in serum testosterone from baseline for the darolutamide arm of less than 45%. Additional non-binding thresholds to help with the decision on the conduct of, or changes in the randomized phase, are that the incidence of feminizing side effects observed is below than that previously reported

Depending on the results of the evaluation and in case of the decision to proceed with the randomized phase, the primary endpoint may be modified, and the statistical assumptions revised. The Sponsor withholds the right to conduct or stop the lead-in phase or start the randomized phase in case data on testosterone levels from patients treated with darolutamide alone would become available from other ongoing studies.

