1.2. Study Design

1.2.1 Overall Design

This is a two-stage open-label phase 2 study with a lead-in single-arm phase and the randomized phase, to assess the impact of androgen receptor inhibitor (ARI) darolutamide or enzalutamide as a monotherapy treatment on serum testosterone levels in men with hormone-naïve prostate cancer experiencing BCR. The study design is shown in Figure 1-1.

Figure 1-1: Overall Design

Abbreviations: ECOG Eastern cooperative oncology group, PC prostate cancer, PSADT PSA doubling time.

In the lead-in phase, participants will be treated with darolutamide (600 mg twice daily). The primary analysis of the lead-in phase will occur when the last participant in the lead-in phase has been on treatment for 12 weeks, unless the participant discontinued due to lost to follow-up, withdrawal, or death. Analysis will be based on a date-based data cut in which the cutoff date will be the last participant week 12 visit date.

The study team will review the findings from the lead-in phase and provide input on interpretation of the results from the lead-in phase. This will help guide a decision on go/no-go with the randomized phase as well as potential changes in the study design for the randomized phase by the sponsor.

In case of the decision to proceed in the randomized phase, participants will be randomized in a 1:1 ratio to receive either darolutamide (600 mg twice daily) or enzalutamide (160 mg once daily). The primary analysis of randomized phase will be conducted when the last participant in the randomized phase has been on treatment for at least 12 weeks. Similar to lead-in phase the analysis will be based on a date-based data cut.

The final analysis for both phases of the study will occur when last participant in the randomized phase has been on treatment for at least 52 weeks, unless the participant discontinued due to lost to follow-up, withdrawal, or death.

The overall sample size across the two phases is expected to be about 65 participants.

The study will comprise the following consecutive periods: Screening, Treatment, and Active Follow–up.

ARAMON V3.0 Page: 9 of 31

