2.1. Multiplicity Adjustment

Not applicable as there are no co-primary endpoints or interim analyses requiring special means for the control of the overall false positive error rate.

ARAMON V3.0 Page: 11 of 31

3. Analysis Sets

For purposes of analysis, the following populations are defined:

Table 3-1: Populations for analyses: Lead-in phase

Population	Description
Screened	All participants who sign the informed consent form
Evaluable	All enrolled participants having testosterone data at baseline and Week 12. Enrolled participants include those who signed informed consent and met all inclusion and none of the exclusion criteria.
Safety	All enrolled participants who received any darolutamide post-enrollment regardless of their eligibility for the study.

Table 3-2: Populations for analyses: Randomized Phase

Population	Description
Screened	All participants who sign the informed consent form
Evaluable	All randomized participants having testosterone data at baseline and week 12 who signed informed consent and met all inclusion and none of the exclusion criteria.
Safety	All randomized participants who received any quantity of study intervention, regardless of their eligibility for the study. The safety evaluation will be performed based on the intervention actually received.

Final decisions regarding the assignment of participants to analysis sets will be made during the review of study data and documented in the final list of important deviations, validity findings and assignment to analysis set(s).

ARAMON V3.0 Page: 12 of 31

4. Statistical Analyses

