4.2.1 Main Analytical Approach

The primary endpoint for the lead-in phase will be analyzed at 12 weeks after start of darolutamide for the last participant in the lead-in phase. If the study continues into the randomized phase, the primary endpoint analysis for the randomized phase will be conducted 12 weeks after start of study treatment for the last participant in the randomized phase.

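### SAP 1.2.1 does not say whose week-12 visit sets the lead-in data cutoff; on the natural reading the cut can precede a late starter's in-window visit, an expected loss of about 0.2 to 0.3 men

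*Protocol*

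**What the plan says.** The two documents time the primary analyses in several ways.

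- Protocol 4.1, lead-in: "when all participants in the lead-in phase have been on treatment for 12 weeks".
- Protocol 9.4, lead-in: the analysis "will occur when the last participant has been on the treatment for at least 12 weeks". Randomized phase: "when all the patients in the randomized phase have been on the treatment for at least 12 weeks".
- SAP 1.2.1, lead-in: the analysis "will occur when the last participant in the lead-in phase has been on treatment for 12 weeks", and "the cutoff date will be the last participant week 12 visit date".
- SAP 1.2.1, randomized phase: "Similar to lead-in phase the analysis will be based on a date-based data cut". No date is named.
- SAP 4.2.1, lead-in: the endpoint "will be analyzed at 12 weeks after start of darolutamide for the last participant in the lead-in phase".

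Protocol Tables 1–3 and 1–4 allow the week-12 visit to be 7 days early or late. The lead-in Evaluable set (SAP Section 3, Table 3-1) is "All enrolled participants having testosterone data at baseline and Week 12", subject to eligibility, and the randomized set has the same data requirement. SAP 4.1.2 rules out estimating missing values or carrying them forward. The SAP version history records that the data-cut detail was added in version 2.0 to make clear which data are analysed, so the sentence is meant to operate.

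**The concern.** A date-based cut excludes any value collected after the cutoff. If the cutoff is the visit date of the last man to start and he is seen early in his window, a man who started a few days before him may still have his own week-12 visit ahead of him, inside his window. His testosterone value would be outside the data cut, and the Evaluable definition would then remove him from the primary analysis.

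The plan would not repair this later. SAP 4.1.1 confines the final lead-in summaries to visits after week 12, and neither document schedules a repeat of the week-12 analysis. The lead-in estimate rests on about 20 men and feeds the binding requirement of a mean rise below 45% before the randomized phase can start. A value that would exist within days should not be left out of it.

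**Working it through.** **1. Window arithmetic.** Week 12 is 12 × 7 = 84 days after first dose, so the window runs from day 77 to day 91. If the last man to start is seen on day 77, the cut is 84 − 77 = 7 days short of 12 weeks. A man first dosed *g* days before him, and seen on his own day 91, is seen 91 − *g* days after the last man's first dose. That is after the cut only if 91 − *g* > 77, that is, if *g* < 14. Men who started 14 or more days earlier are not exposed.

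**2. Men exposed.** Protocol 1.4.1 gives enrolment periods of 6 and 12 months (the 6 months is tied there to 20 evaluable men; all 25 are spread over it here). With even enrolment:

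- Lead-in: 25 × 14 / 182 = 1.9 men
- Randomized: 40 × 14 / 364 = 1.5 men

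**3. Expected loss.** Let *r* be the enrolment rate per day, and let *D* be the difference between two men's visit deviations from day 84. The expected number of visits after the cut is about *r* × E[max(*D*, 0)].

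- Deviations uniform over ±7 days: E[max(*D*, 0)] = 14/6 = 2.33 days.
- Deviations normal with SD 3 days: *D* has SD 3√2 = 4.24, and E[max(*D*, 0)] = 4.24/√(2π) = 1.69 days.

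The spread of visit days is an assumption, because the documents give only the window. The last column comes from simulation with no dropout.

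| Phase | Visit days | *r* × days | Men lost | Chance of ≥1 |
|---|---|---|---|---|
| Lead-in | uniform | 0.137 × 2.33 | 0.32 | 25% |
| Lead-in | SD 3 | 0.137 × 1.69 | 0.23 | 19% |
| Randomized, same rule | uniform | 0.110 × 2.33 | 0.26 | 21% |
| Randomized, same rule | SD 3 | 0.110 × 1.69 | 0.19 | 16% |

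Counting in whole days, with same-day visits inside the cut, lowers these slightly: 0.31 (24%) and 0.20 (17%) in the lead-in, 0.25 (20%) and 0.16 (14%) in the randomized phase. In the extreme case, with the last man at −7 days and everyone else at +7, the means are those of step 2.

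**4. Other cutoffs, same assumptions.**

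- Latest week-12 visit of any man: none lost.
- Last first dose plus 84 days, in the spirit of SAP 4.2.1: mean 0.69 (lead-in) and 0.65 (randomized), with uniform whole-day visits. This is worse, because the last man himself can be lost.
- Last first dose plus 91 days: no in-window visit lost.

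**5. Effect on precision and power.** First the plan's own figures.

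- *Lead-in half-width, stated as at most 25%.* The log-scale SD is √ln(1 + (0.65/1.45)²) = 0.428. Taking 45% as the arithmetic mean, the geometric mean fold change is 1.45 × exp(−0.428²/2) = 1.323. With *h* = 1.96 × 0.428/√20 = 0.1875, the half-width is 100 × 1.323 × (e^h − e^−h)/2 = 25.0 points, which reproduces the plan. At 19 men it is 25.6. With t quantiles the pair is 26.7 and 27.5.
- *Power, stated as 85% at 20 per arm.* The SDs are 0.428 and √ln(1 + (0.75/2.10)²) = 0.346, root mean square 0.389; the difference is ln(2.10/1.45) = 0.370. Power = Φ(0.370/(0.389√(2/20)) − 1.96) = 85.3%, which reproduces the plan. At the 17 per arm implied by 34 evaluable men it is 79.2%. Losing one man per arm (16) gives 76.8%.

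**The case against.** The strongest reply is that the cutoff phrase can mean the latest week-12 visit among all men. Both documents use the parallel term, last patient last visit, in that sense: Protocol 4.3 and SAP 1.2.3 treat it as reached only when everyone has finished. Protocol 4.1 also waits for all lead-in participants. On that reading nobody is lost, and this stands. It is the less natural reading, because the SAP sentence just before the cutoff speaks of one man's time on treatment and SAP 4.2.1 counts from that man's start. That both readings are open is a reason to define the term.

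Two further replies stand. The last man is not lost by being seen on day 77, since his value is a valid in-window one. And the expected loss is small beside the allowances of 25 − 20 = 5 and 40 − 34 = 6 men.

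A reader might infer more than the documents support:

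- *That early stopping by the last man leaves no cutoff date.* Men who only stop treatment stay in active follow-up (Protocol 4.1.3 and Section 7), and Table 1–5 schedules their week-12 testosterone visit. The gap is confined to withdrawal, death or loss to follow-up. SAP 1.2.1 exempts those cases from the lead-in timing trigger but names no substitute date.
- *That the randomized phase has the same defect.* The SAP gives that phase no cutoff date and keeps at least 12 weeks in its trigger. The randomized figures apply only if *similar* means the same rule.
- *That the open-label design makes the cut a source of bias.* The endpoint is a laboratory value (Protocol 6.4), and nothing in the documents points to visit timing being chosen by result.

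**Conclusion.** The point holds as a minor defect of definition. On the natural reading, the lead-in cutoff can fall up to 7 days before the protocol's 12 weeks and before the in-window visit of a man first dosed less than 14 days before the last starter. The expected cost is about 0.2 to 0.3 men in the lead-in, with about a 19% to 25% chance of losing at least one (17% at the low end if counted in whole days). It is about 0.2 to 0.25 men in the randomized phase if the rule carries over. These figures assume even enrolment, no dropout and the visit-day spreads shown; bunched late enrolment would raise them. One man lost at the planned 20 widens the lead-in interval by about 0.6 points. The sample size and power statements are unaffected. On the alternative reading the loss is zero.

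**What to change.** In SAP 1.2.1, for each phase, define the cutoff as the latest first-dose date among all participants in that phase plus 91 days, whatever that participant's status by then. This closes every week-12 window, meets the 12-week trigger, and gives a date that is known once the last man is dosed and still exists if he withdraws, dies or is lost. Anchoring on the latest first dose, not on the last man enrolled, matters because enrolment precedes dosing. Only a visit outside its window could still fall after the cut.

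Align SAP 4.2.1 and the timing wording in Protocol 4.1 and 9.4 with this rule. Adopting SAP 4.2.1's 12 weeks as the cutoff would not solve the problem. The cost is one SAP sentence and the matching edits; the cut moves later by at most about two weeks (day 77 to day 91).
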